### D3. The CONTROL – information prescriptions to refer to patients

#### 1. Hygienist Control – Information Prescriptions

In planning this proposal, we considered several potential controls as suggested by the framework for evaluating complex

interventions. In DTC.Net, we are currently using a wait-list control group. Control providers will have access to the full intervention after data collection is complete. Thus, control hygienists are delivering “usual care.” However, for this intervention, we felt that a wait-list control ignores other recent advances in provider referrals to self-management in smoking cessation (i.e.: information prescriptions).

Also, although we have not had differential attrition in the wait-list control, compared with intervention, in DTC.Net, anecdotally, control providers have expressed concerns about having “nothing new” to provide to patients. We are concerned about the threat of long-term wait-listing to overall retention in the control group. Specifically, we want to test the uniqueness of the integration clinical microsystem intervention. After consideration, we have chosen a more active, symmetric control reflecting recent offline research into provider referrals. Thus, our control group provides parallel interventions – for providers and then patients – that are *not* integrated.

We have chosen an “information prescription” control. Providers in the control group will be provided preprinted pads of “information prescriptions” with their office information, motivational messages for patients, a space for the provider to sign, and the control website address.

The information prescription pads also have an important role in our analysis. The pads will have numbered leave-behind receipts used to tally the number of referrals issued. These pads will be collected from the control practices to obtain an accurate account of the number of patients referred. The control group will not have access to 1) HI-QUIT Help Desk, 2) Refer2Quit portal at the point of care; 2) Feedback Reports of patient activity; 4) automated email reminders for patients and providers; 5) HI-QUIT content updates and linking functions.

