We will approach this analysis in two ways. In both approaches, the numerator will be the number of patients who report cessation at six-month follow-up calls. In our primary analysis, we will use an intent-to-treat analysis in that we will include all practices (regardless of whether they actually use the intervention) and will include all smokers who are referred (the same denominator used in H1) regardless of whether they GO to the website. This represents a conservative assessment since we assume that many patients will not GO, and for the purposes of analyses, we will assume that these patients will not have quit. The most conservative analysis would be to use the total number of smokers seen in the practices as the denominator. However, we will not know this number exactly. Our exit cards give an estimate but we do not have a continuous measure of total smokers.

As a secondary analysis, we will assign the denominator as the number of patients who GO to the website. For this secondary analysis, consistent with current guidelines for smoking cessation trials, we will assume that patients who are lost to follow-up, including those who GO and do not agree to follow-up, are smokers.

We have assumed a control cessation rate of 17% among those with completed cases (follow-up complete) in the control group based on a range of completed case and intent-to-treat evaluations of prior internet smoking cessation interventions (Table 11). For the purposes of power calculations, we estimate

**Table 11:** Six-month cessation anticipated among completed cases, those who go to the website, and those referred from 80 practices.

	Six-month cessation among Completed Cases*†		Cessation among those who GO		Cessation among those who are referred‡ (Primary Analysis)	
	n/N	Proportion	n/N	Proportion	n/N	Proportion
Intervention	120/456	26%	120/760	16%	120/1920	6%
Control	20/120	17%	20/200	10%	20/960	2%

\* Completed Cases are those with completed six-month telephone surveys  
 † Assumes 60% follow-up among those who GO (see Table 8 for number who go per practice) and assigns not abstinent to those without follow-up  
 ‡ Assumes those who are referred and do not go are **not abstinent**, based on estimates of those referred from Table 8 multiplied by the number of practices

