**Hypothesis 2:** This analysis will test the proportion of patients referred who GO to the website, comparing HI-QUIT practices and control practices. As discussed above, a conservative base rate for control practices is for 12% of smokers to be referred and for approximately 20% of those to GO to the website. We expect these proportions to increase for the intervention group to 24% and 40%, respectively. We then need to examine statistical power to detect a 20% difference (40%-20%) in the proportion of referred patients who GO between the two groups, which corresponds to an odds ratio of 2.8. Based on approximately 200 smokers per practice per year and the referral rates above, we expect averages of 24 and 48 smokers to be referred from each control and intervention practice, respectively (Table 8).

Because of the group randomization, our effective sample size must again be reduced by a design factor for each group. Because "GO" to the website is more patient-directed, we have assumed a lower ICC of 0.05 for this analysis. Conservatively assuming an ICC of 0.05, we calculated design factors of 2.2 and 3.6 for the control and intervention groups, respectively. Incorporating the design factors gives an effective sample size per practice of 12 for the control group and 14 for the intervention group. Using a two-sided chi-square test with Type 1 error rate of 0.05, only 10 practices per arm are required to achieve 80% power. If we assume a smaller effect where only 30% of referred smoker in the intervention group GO, 30 intervention practices and 30 control practices are sufficient to achieve 80% power.

**Hypothesis 3:** This analysis of patient cessation outcomes is again conducted at the patient level. As detailed in the analysis plan we will approach this hypothesis in two ways and power calculations will be presented for each. For both approaches, this hypothesis will be tested as a two-sided chi-square test for equality of proportions and the number who quit will be assessed at follow-up among those who visited the website.

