As the primary analysis, and most conservative approach, we will test whether those patients referred through HI-QUIT are more likely to quit than control patients who received information prescription referrals. As in H1), we expect 48 referrals from each intervention practice and 24 from each control practice. Based on ICCs from DTC.Net, we will use an ICC of 0.017 to account for clustering within practices. We further again assume that 20% of referred control patients will GO as will 40% of referred intervention patients. We will

Principal Investigator/Program Director (Last, First, Middle): DPBRN c/o [name]

assume that the cessation rate was 0% among those referred who did not GO. Assuming an intent-to-treat cessation rate of 10% among control patients who GO and 15% for the intervention group (See Table 11), we arrive at overall cessation rates of 2% for the control group and 6% for the intervention group. Only 8 practices per group are required to achieve 80% power to test this hypothesis with a Type 1 error rate of 0.05. If power is reduced by assuming that only 30% of referred intervention group smokers GO, 36 practices per group are required for 80% power.

In summary, evidence suggests that there is ample power to detect clinically significant differences for the three main hypotheses with conservative assumptions.

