For patients referred by hygienists using refer to quit, patient consent is layered and matched to the risk and burden to the patient. Patient consent is not obtained at chairside after they agree to be enrolled. At this level of participation, only patient email is collected. Intervention patients will receive emails after being referred to the intervention website by providers. To minimize risk, the emails will only contain a reminder to go to the website, but will not identify the purpose of the website. No personal health information will be in the emails. Because risk is low and it is not feasible to obtain informed consent without changing the processes of care themselves, we will not obtain informed consent at this level (similar to prior Fax-to-Quit studies).

If patients choose to log onto the web-based system, they will be asked to complete an online consent process where they agree to specific line items (agree to allow us to track their use of the site, agree to follow-up) by online check boxes verified with a username and password they create. If they agree, they will provide telephone numbers for follow-up. If they do not wish to participate in follow-up, they can use the online system without providing additional identifying information. Because participation is again optional, and because requiring written consent would likely greatly decrease use of the online system, we will not obtain written informed consent at this phase. Once the patient is called for follow-up, we will complete a verbal consent procedure for participating in the interview. If the patient reports smoking cessation, we will obtain written informed consent when the specimen is collected. Thus, signature documentation is only obtained for the subset of patients for whom biologic specimens are obtained. This layered procedure has been used in prior studies including DTC.Net and the NCI-funded Smoking Coach study referenced in the application.

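### H3 can record a quit only in patients who log on, and logging on is planned at 40% versus 20%, so scoring all others as smokers is not conservative for the between-arm difference

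*Protocol*

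**What the plan says.** The protocol's section D9 (Data Definitions for H3) sets two approaches, and in both "the numerator will be the number of patients who report cessation at six-month follow-up calls". The primary analysis takes all referred smokers as the denominator. Of those who do not GO it says "for the purposes of analyses, we will assume that these patients will not have quit", and it justifies this with "This represents a conservative assessment since we assume that many patients will not GO". Section D9 repeats the label for the rates carried into the power calculation, and section D10 (Hypothesis 3) calls the approach the most conservative one.

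D10 confirms that "the number who quit will be assessed at follow-up among those who visited the website" and that the investigators will "assume that the cessation rate was 0% among those referred who did not GO". It plans that "20% of referred control patients will GO as will 40% of referred intervention patients".

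No route exists to learn the smoking status of a patient who does not GO. Telephone numbers come only from patients who log on and agree to follow-up (Patient Recruitment Part 2; section E). Of intervention patients at referral, section E says "At this level of participation, only patient email is collected". Of control patients the practice keeps only a receipt (D3): "The pads will have numbered leave-behind receipts used to tally the number of referrals issued".

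**The concern.** Scoring unobserved patients as smokers lowers the recorded rate in each arm. It protects the comparison only if the unobserved share is similar in both arms, or larger in the intervention arm. Here the unobserved share is the complement of the H2 outcome, which direct enrolment and e-mail reminders are meant to change. The plan itself expects to lose sight of 80% of control referrals and 60% of intervention referrals through non-GO alone.

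H3 is one of three primary outcomes and the only one about cessation. As defined, it cannot separate more patients logging on from more patients quitting. A significant H3 could partly restate H2, while the word *conservative* would invite readers to take it as a lower bound.

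**Working it through.** **Inputs from the protocol.** GO 40% and 20%, cessation among GO 15% and 10% (non-followed-up counted as smokers), 48 and 24 referrals per practice, ICC 0.017, two-sided alpha 0.05 (D10). Completed-case control rate 17% and 60% follow-up among GO (D9). 30 to 40 practices per arm completing follow-up (Anticipating attrition). **Assumption:** the true quit rate of referred patients when there is no effect. The documents give none for non-GO patients, so a range is shown.

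**1. The plan's own figures.** Recorded rate = P(GO) × P(recorded quit given GO).
- Control: 0.20 × 0.10 = 2.0%. Intervention: 0.40 × 0.15 = 6.0%. Both match D10.
- Table 11: 20/960 = 2.1% and 120/1920 = 6.25%.

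**2. No cessation effect, one common true quit rate r.** Control records 0.20 × 0.60 × r = 0.12r; intervention records 0.40 × 0.60 × r = 0.24r. The true difference is zero, but the recorded ratio is 2 for any r above zero.

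**3. How often H3 would then be significant.** Design effects are 1 + 47 × 0.017 = 1.799 (intervention) and 1 + 23 × 0.017 = 1.391 (control). Effective sizes per practice are 48/1.799 = 26.7 and 24/1.391 = 17.3. That gives about 800 and 518 at 30 practices per arm, and 1,067 and 690 at 40. Rejection probability = Φ((d − 1.96·SE₀)/SE₁), where d is the recorded difference, SE₀ its pooled and SE₁ its unpooled standard error.

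| No-effect scenario | Intervention | Control | 30 per arm | 40 per arm |
|---|---|---|---|---|
| r = 5% | 1.20% | 0.60% | 18% | 23% |
| r = 10% | 2.40% | 1.20% | 33% | 43% |
| r = 17% | 4.08% | 2.04% | 53% | 66% |
| 20% who GO in either arm quit at 17%; extra 20% prompted to GO quit at 5% | 2.64% | 2.04% | 10% | 12% |

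The last row is 0.60 × (0.20 × 0.17 + 0.20 × 0.05) against 0.60 × 0.20 × 0.17. The nominal level is 5%. A beta-binomial simulation with a cluster-robust test gave somewhat higher figures: 40% and 50% at r = 10% (30 and 40 per arm). With equal ascertainment in both arms it gave 4.9% and 4.8%.

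**4. Background rate q at which the planned result loses significance (Table 11 rates).**
- Applied to everyone without an observed status (non-GO, and GO without follow-up): control 0.0208 + 0.88q, intervention 0.0625 + 0.76q, since 0.80 + 0.20 × 0.40 = 0.88 and 0.60 + 0.40 × 0.40 = 0.76. At q = 9% the rates are 10.0% and 13.1%, and z = 1.95 at 40 per arm. At 30 per arm the same point comes at about 7% (8.2% and 11.6%, z = 1.94). The difference reaches zero only at 0.0417/0.12 = 35%.
- Applied to non-GO patients only: control 0.0208 + 0.80q, intervention 0.0625 + 0.60q. At q = 7% the rates are 7.7% and 10.5%, and z = 1.94 at 40 per arm. The difference reaches zero at 0.0417/0.20 = 21%.

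**5. Whether another planned analysis repairs it.** The secondary H3 analysis conditions on GO. The adjusted model (D9, Analyses for H3) uses readiness entered on the website, so it is unknown for non-GO patients. The pattern-mixture work in D8 concerns cotinine return and misclassification. None addresses smoking status in non-GO patients.

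**The case against.** Five points deserve weight.

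- **Raising GO is the intended route to quitting.** If using the website causes quits, the part of the difference that runs through higher GO is treatment effect. A reader might infer from 0.40 × 0.10 = 4% versus 0.20 × 0.10 = 2% that half of the planned effect is artefact. That holds only if the website causes no quits, which the documents do not show.
- **17% is a high rate for all referred smokers.** It describes website visitors who completed follow-up, a group selected twice, in a trial that also takes smokers not trying to quit. A reader might take the 66% in the last column as the false-positive rate of H3. It is the upper end of a range, at the most favourable number of practices. A larger figure from the unadjusted chi-square would mix in a separate problem, ignored clustering.
- **The secondary analysis would give a warning.** With a common 17% and no effect, both arms would show 0.60 × 0.17 = 10.2% among GO. That helps interpretation, but conditioning on GO is conditioning on behaviour after randomisation, so it does not repair the primary analysis.
- **Other biases may run the other way.** The protocol notes that control pads may be lost (shrinking the control denominator) and that control referral may be more selective. Both could raise the recorded control rate. Nothing shows that they cancel the ascertainment imbalance.
- **A sensitivity analysis may sit in an SAP that is not shown.** That is possible, and its absence is not the fault raised here. The fault is the protocol's own statement that the rule is conservative.

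The first two points limit the size. None changes the direction of this source of bias.

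**Conclusion.** The rule is wrongly described. It is conservative for each arm's absolute quit rate. If GO differs as planned and non-GO smokers quit at all, it biases the between-arm difference toward the intervention. If non-GO patients truly never quit, or GO did not differ by arm, this source of bias would vanish; the protocol gives no evidence for the former and plans against the latter.

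The size rests on an assumed quit rate. With no cessation effect, a significant H3 would occur in roughly 10% to 66% of trials across the scenarios shown, against a nominal 5%. These figures treat this bias alone, before any offset. Under the planned rates the difference stays positive for background rates up to 17%, but significance is lost at about 9% at 40 practices per arm (about 7% if the rate is applied to non-GO patients only). The documents do not support saying that H3 would be a false finding; they support saying that H3 as defined cannot establish a cessation effect without a check on this assumption.

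**What to change.** 1. Remove *conservative* as a description of the H3 comparison in D9 and D10. It may stay as a description of the absolute rates.
2. Define the primary H3 endpoint as documented quits among referred patients.
3. Pre-specify beside it a cluster-adjusted analysis that applies one common background quit rate, in both arms, to all patients without an observed status (non-GO, and GO without follow-up). Vary it from 0% to 17%, the plan's completed-case control rate, and report the rate at which significance is lost.
4. Word any conclusion about cessation according to that result.

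A question about quitting on the exit cards would not help: the cards are anonymous and carry no patient follow-up, so they cannot identify referred smokers at six months.

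The cost is a change of wording and one extra analysis, with no new data collection. The downside is a narrower H3 claim.

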### **Qualitative Process Analysis – How Practice Characteristics Impact Use of the Referral System:**

Case-Comparison study - Our main analyses above are to test overall differences, Intervention versus Control. However, based on our prior experience, adoption of the intervention will vary. Some hygienists and practices will have high rates of referral and, despite our efforts, some practices may use Refer2Quit very little. Consistent with the framework for evaluation of complex interventions, we plan a second qualitative analysis to answer questions including: What organization and process factors are related to adoption, or not adoption, of the intervention? To accomplish this task, we plan to conduct semi-structured interviews with a random sample of providers.

The design is a case-comparison study, a subset of the multimethod assessment process (MAP).

Sample: We will use a selective sampling strategy. Selective sampling is defined as sampling subjects according to a preconceived, but reasonable initial set of criteria to obtain a broad array of informants. As the goal of our qualitative research is to obtain a range of opinions related to workflow processes, barriers, facilitators and other themes related to adoption, we will target specific practices and providers. Our first layer of selective sampling is to identify 1) high and 2) low-adopting practices. We also would like to obtain larger and smaller practice sizes. Thus, we will interview hygienists and dentists from an initial random sample of 8 high and 8 low-adopting practices among the 40 intervention practices (also split by large and small practice size).

Many qualitative research studies use a combination of selective sampling and theoretical sampling. We will conduct iterative analyses and may find that we do not reach theme saturation in some strata of our selective sampling after 16 practices. We have budgeted resources for up to 20 practices to provide for the needs of theoretic sampling and theme saturation.

Interviews - We will develop a Semi-Structured interview guide. The interview guide will be reviewed by our team and two participating practices that are not top adopters. The interview guides will be developed to encourage participants to “tell the story” of how patients receive care. DPBRN Coordinating Center staff will recruit and conduct the semi-structured interviews. Our goal will be three telephone interviews per practice. A verbal consent will be obtained and the interview will be recorded.

Analysis - Interviews will be transcribed and anonymized. Because one of primary goals is to describe the processes of care, we will use a combination of thematic summary and narrative summary. Narrative summary is best used when qualitative data follow a logical order (such as patient care) and frequently used in triangulation with quantitative data. The transcribed interviews will be reviewed by two independent reviewers ([name], [name]) to develop preliminary themes. To develop themes, we will use an open-coding approach to be maximally inclusive. Each open-ended question in the interview guide will be assessed separately, and then the reviewer will generate larger summary themes for the overall interview. The themes will then be reviewed with the larger investigator group in the steering committee meeting to resolve disagreements. From the themes, we will create summary tables of key points. We will complete this method twice while collecting interviews. In this way, we will assess for theme saturation and further revise our data collection methods for the second wave of interviews to focus on details of interest.

**D10. Power Calculations** - All power calculations were made using nQuery Advisor v.6.01, and the primary analysis are carried out at the patient-level with sample sizes adjusted for the clustering of patients within practices. To do this, we used practice-level Intraclass correlations derived from DTC.Net. For all power calculations, we have built in two **conservative assumptions** that impact our power calculations.

Principal Investigator/Program Director (Last, First, Middle): DPBRN c/o [name]

- 1) We have estimated the power based on one year of access, but the intervention will actually have availability for 20-months, thus number of smokers referred will be somewhat higher.
- 2) We assume that only two providers per practice will be actively involved in referring patients. Thus, for some practices more providers may participate and the number of patients referred (say if four hygienists and dental assistants refer) may be considerably greater.

**Hypothesis 1:** This analysis will test whether HI-QUIT practices refer patients at a higher rate than control practices. The literature supports estimating the mean baseline referral rate of 12% for control practices.

Power was estimated using a two-sided chi-square test for a difference in proportions with a Type 1 error rate of 0.05. To take a conservative approach, power was calculated assuming an average of 66 smokers per practice responding to the exit cards. Due to

H1: Number of subjects needed per group for 80% power with a two-sided $\chi^2$ test of equal proportions and $\alpha=0.05$ , adjusting for clustering in practices				
	1	2	3	4
Control proportion, $\pi_1$	0.12	0.12	0.12	0.12
HI-QUIT proportion, $\pi_2$	0.24	0.22	0.20	0.19
Unadjusted n needed per group	176	240	354	447
Adjusted n needed per group*	1,892	2,580	2,805	4805
Number of practices needed per group	29	39	58	73

\* Design factor (  $D = [1 + (m-1) r]$ ) inflates n to account for clustering

clustering within practices and clustering within providers, these will not all be independent observations. The standard practice is to adjust the sample size by an inflation factor  $D = [1 + (m-1) r]$  where r is the intra-class (practice-level) correlation (ICC) and m is the number of subjects per group (practice). Pilot data from DTC.Net revealed a relatively large ICC of 0.15 for rates of advice to quit smoking within dental practices. Assuming equal ICCs of 0.15 for Refer and a cluster size of 66 smokers per practice gives  $D= 10.75$ , or an effective sample size per practice of approximately 6 patients. With these numbers only 29 practices per arm are required to achieve 80% power to detect a significant difference in referral rates of 0.12.

**Hypothesis 2:** This analysis will test the proportion of patients referred who GO to the website, comparing HI-QUIT practices and control practices. As discussed above, a conservative base rate for control practices is for 12% of smokers to be referred and for approximately 20% of those to GO to the website. We expect these proportions to increase for the intervention group to 24% and 40%, respectively. We then need to examine statistical power to detect a 20% difference (40%-20%) in the proportion of referred patients who GO between the two groups, which corresponds to an odds ratio of 2.8. Based on approximately 200 smokers per practice per year and the referral rates above, we expect averages of 24 and 48 smokers to be referred from each control and intervention practice, respectively (Table 8).

Because of the group randomization, our effective sample size must again be reduced by a design factor for each group. Because "GO" to the website is more patient-directed, we have assumed a lower ICC of 0.05 for this analysis. Conservatively assuming an ICC of 0.05, we calculated design factors of 2.2 and 3.6 for the control and intervention groups, respectively. Incorporating the design factors gives an effective sample size per practice of 12 for the control group and 14 for the intervention group. Using a two-sided chi-square test with Type 1 error rate of 0.05, only 10 practices per arm are required to achieve 80% power. If we assume a smaller effect where only 30% of referred smoker in the intervention group GO, 30 intervention practices and 30 control practices are sufficient to achieve 80% power.

**Hypothesis 3:** This analysis of patient cessation outcomes is again conducted at the patient level. As detailed in the analysis plan we will approach this hypothesis in two ways and power calculations will be presented for each. For both approaches, this hypothesis will be tested as a two-sided chi-square test for equality of proportions and the number who quit will be assessed at follow-up among those who visited the website.

As the primary analysis, and most conservative approach, we will test whether those patients referred through HI-QUIT are more likely to quit than control patients who received information prescription referrals. As in H1), we expect 48 referrals from each intervention practice and 24 from each control practice. Based on ICCs from DTC.Net, we will use an ICC of 0.017 to account for clustering within practices. We further again assume that 20% of referred control patients will GO as will 40% of referred intervention patients. We will

Principal Investigator/Program Director (Last, First, Middle): DPBRN c/o [name]

assume that the cessation rate was 0% among those referred who did not GO. Assuming an intent-to-treat cessation rate of 10% among control patients who GO and 15% for the intervention group (See Table 11), we arrive at overall cessation rates of 2% for the control group and 6% for the intervention group. Only 8 practices per group are required to achieve 80% power to test this hypothesis with a Type 1 error rate of 0.05. If power is reduced by assuming that only 30% of referred intervention group smokers GO, 36 practices per group are required for 80% power.

In summary, evidence suggests that there is ample power to detect clinically significant differences for the three main hypotheses with conservative assumptions.

